1.3 Schedule of Activities

Table 3. Schedule of activities.

Tests and Procedures	Procedures for Patients Completing the Study						Procedures for Early Termination or Withdrawal			
	Screening / Baseline	Day 1 [†]	Study Treatment Period (Days 2 – 29)	Discharge contact [‡]	Day 29 contact ^{**}	Day 60 Follow-up ^{***}	Early Termination / Withdrawal	Discharge contact [‡]	Day 29 contact ^{**}	Day 60 Follow-up ^{***}
	0 to 4 days before Day 1	(Visit 1) all pre-dose	Daily until hospital discharge or Day 29, whichever is first (or as noted)	(7 ± 3 days)	(29 ± 3 days)	(60 ± 5 days)		(7 ± 3 days)	(29 ± 3 days)	(60 ± 5 days)
Written Informed Consent	X									
Demographics	X									
Record medical history and hospital admission data	X									
Brief physical exam*	X									
Safety laboratory tests hematology, chemistry (non-fasting), urinalysis, serology, pregnancy test (as applicable) [‡]	X		At discharge or on Day 29 [‡]				X			
Review Inclusion/Exclusion criteria and categorize disease severity	X									
Randomization		X								
Vital signs including oxygen saturation [‡]	X	X	X ¹				X ¹			
7-point ordinal scale assessment [‡]	X	X	X ¹	X	X	X	X ¹	X	X	X
Record SoC concomitant medication and treatments	X	X	X				X			
Record SoC laboratory test results (e.g., hematology, chemistry, serology, pathology, radiology, urinalysis, etc.) [^]	X	X	X				X			
Adverse Events assessment	X	X	X	X	X	X	X	X	X	X
Dispense blinded study medication and record		X	On Days 12 and 24							
Collect used, blinded study medication and record			On Days 12, 24 and 29 (or discharge)				X			
Study medication training and observation and record		X								

Tests and Procedures	Procedures for Patients Completing the Study						Procedures for Early Termination or Withdrawal			
	Screening / Baseline	Day 1 [†]	Study Treatment Period (Days 2 – 29)	Discharge contact [‡]	Day 29 contact ^{**}	Day 60 Follow-up ^{***}	Early Termination / Withdrawal	Discharge contact [‡]	Day 29 contact ^{**}	Day 60 Follow-up ^{***}
	0 to 4 days before Day 1	(Visit 1) all pre-dose	Daily until hospital discharge or Day 29, whichever is first (or as noted)	(7 ± 3 days)	(29 ± 3 days)	(60 ± 5 days)		(7 ± 3 days)	(29 ± 3 days)	(60 ± 5 days)
Dose blinded study medication with study staff and record [‡]		X	twice daily (morning and evening) until discharge or Day 29 ²				X ²			

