Follow-up vital status				X	X	X		X	X	X
Re-hospitalization/Still in hospital status				X	X	X		X	X	X
Vital records search, if needed						X				X
[†]	Day 1 may take place on the same day as the screening/baseline visit, if appropriate. If Day 1 activities take place on the same day as screening/baseline visit, only 1 ordinal scale assessment and vital sign assessment are necessary, but they must be completed prior to dosing.									
[‡]	Discharge Contact: contact with the patient will take place 4 to 10 days after discharge from hospital within the 29-day treatment period. If the patient remains hospitalized after Day 29, contact with the patient will take place 4 to 10 days after receipt of last dose of study medication on Day 29.									
^{**}	Day 29 Contact (if patient discharged prior to Day 29): contact with the patient will take place 26 to 32 days after first dose of study medication. If the Discharge Contact and Day 29 Contact fall within same window, this contact will be combined as the Day 29 Contact.									
^{***}	Day 60 Follow-up: contact with the patient will take place 55 to 65 days after first dose of study medication.									
[*]	Record the physical exam documented by the treating team on the day of screening, and verify key parts (heart, lung).									
^Ω	If kidney (creatinine), liver (alanine aminotransferase or aspartate aminotransferase) and pregnancy (if applicable, via serum) were not run prior, they are required during the screening process. Refer to exclusion criteria in Section 5.2 and Appendix 3 .									
^β	Discharge safety laboratory tests may be completed at the discretion of the treating physician and, if completed, may be completed within 24 hours of the patient’s discharge from the hospital.									
[¥]	Vital signs should be recorded each morning at approximately the same time of a given study day. Variables: Respiration rate (per minute), Oxygen saturation (SpO2), Any supplemental oxygen (yes/no), Body temperature, Systolic blood pressure, Heart rate (pulse rate per minute); and Level of consciousness graded on the AVPU scale (Alert, Verbal = voice response present, Pain = pain response present, Unresponsive). Refer to Section 8.1.3 .									
¹	These assessments are not required to be completed prior to morning blinded study medication dosing.									

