8.1 Collection of Data

Patients will be assessed daily while hospitalized. Clinical data will be recorded using eCRFs adapted from the WHO-ISARIC (World Health Organization–International Severe Acute Respiratory and Emerging Infections Consortium) case record form (<https://isaric.tghn.org>).

Screening and baseline information will be collected and recorded on the eCRF. This will include the following information:

- Informed consent review, eligibility review, including screening liver, kidney and pregnancy (if applicable) laboratory tests, and categorization of their positive COVID-19 disease severity (according to the FDA’s document: COVID-19: Developing Drugs and Biological Products for Treatment or Prevention Guidance for Industry, May 2020). Refer to [Section 8.1.2](#) for severity definitions.
- Demographics, hospital admission date (for COVID-19 infection), medical and smoking history, standard of care medications and treatments and type of facility transferred from.
- Existing co-morbidities and any medication taken for those listed as well as medications taken since admission.

Randomization information will be recorded on an eCRF. If study medication is dispensed, it will be recorded on this form.

Starting on Day 1 to discharge, Day 29 or withdrawal of consent, site staff will record on an eCRF daily the following information:

- Clinical status (7-point ordinal scale) each morning ([Section 8.1.1](#)).
- Vital signs each morning at approximately the same time ([Section 8.1.3](#)).
- Concomitant medications taken as part of SoC for COVID-19 infection treatment ([Section 6.5.1](#) and [Section 8.1.4](#)).
- Supportive treatments received as part of SoC for COVID-19 infection treatment or new infection that develops while hospitalized ([Section 8.1.4](#)).
- Routine laboratory, infection and imaging test results received as part of SoC ([Section 8.1.4](#)).
- Study medication doses taken and when.
- On the day of discharge or Day 29, safety laboratory tests may be performed at the discretion of the treating physician and, if completed, may be completed within 24 hours of the patient’s discharge from the hospital.
- Adverse events.

At discharge site staff will schedule a follow-up and complete an eCRF page including the following:

- Date of discharge and reason (e.g., COVID-19 negative, improved enough for discharge, etc.)
- Where the patient was discharged to (e.g., home, rehab center, etc.)

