8.5 Post Discharge/Day 29 Contacts

Following Day 29 or discharge from the hospital (if earlier), there will be three points of contact with all study patients, regardless of hospitalization status. Each contact will require the completion of a Follow-up eCRF (**Table 15**).

- Discharge Contact: 4 to 10 days after discharge from hospital, if discharged within the 29-day treatment period.
 - If the patient remains hospitalized after Day 29, study treatment and data collection procedures still end on Day 29 (with the exception of contacts in this section) and contact with the patient will take place 4 to 10 days after receipt of last dose of study medication (Day 29).
- Day 29 Contact: 26 to 32 days after first dose of study medication. If the Discharge Contact and Day 29 Contact fall within same window, this contact will be combined to the Day 29.

- Day 60 Follow-up: 55 to 65 days after first dose of study medication.
 - Should a patient or their medical contact be unable to be contacted at any of these timepoints, a vital records search will be performed to determine the patient’s vital status approximately 60 days after first dose of study medication.

Table 15. Post-discharge follow-up activities.

Assessment	Information
Follow-up date	
 • Date of follow-up contact
Clinical status assessment (7-point ordinal scale)	
 • Assessed and documented, as above for Day 1 (clinical and vital status)
Re-hospitalization status or remains in hospital	
 • Any incidence of re-admission to the hospital following a 24-hour period of discharge (date and duration) that is related to COVID-19 • Date of discharge (if after Day 29) should be noted in the Follow-up eCRF.
Adverse Events assessments	
 • Documented, as above for Day 1

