	All-cause mortality at Days 29 and 60.	Clinical status assessed using the 7-point ordinal scale score.
		Death = 7-point ordinal scale score is equal to 7 or using a vital records search returns a death record, the date on the record will be the date of death.
	Proportion of patients alive and not in respiratory failure (invasive mechanical	Clinical status assessed using the 7-point ordinal scale score.
	ventilation or extracorporeal membrane oxygenation (ECMO)) at Days 7, 14 and 29.	The proportion of patients in each treatment arm that meet the definition of alive and not is respiratory failure.
		Alive and not in respiratory failure (invasive mechanical ventilation or ECMO) = 7-point ordinal scale score is equal to 1, 2, 3, 4 or 5.
	Proportion of patients needing re-hospitalization (post-dose Day 1 – Day 60).	Assessed following discharge: the eCRF question regarding re-hospitalization will be used at Day 29 and Day 60 follow-up contact.
		The proportion of patients in each treatment arm that meet the definition of re-hospitalization following discharge.
		Re-hospitalization = following their treatment with study medication and subsequent discharge from hospital, they were re-admitted to a hospital for COVID related issue(s).

pg. 15 Confidential

Endpoints		Definitions
	Total time of hospitalization	Clinical status assessed using the 7-point
	between Day 1 - Day 29 (measured in days).	ordinal scale score.
	(Hospitalized = # days where the 7-point ordinal scale score is equal to 3, 4, 5 or 6.
		Or 7-point ordinal scale score is equal
		to 7 if patient dies while hospitalized
		between Day 1-29.
	Change from baseline in 7-	Clinical status assessed using the 7-point
	point ordinal scale (Days 7, 14 and 29).	ordinal scale score.
		The mean change from baseline of the 7-point
		ordinal scale in each treatment arm as
	Total time on supplemental	assessed by the statistical analysis. Clinical status assessed using the 7-point
	oxygen (Day 1 - Day 29; measured in days).	ordinal scale score.
	. ,	Hospitalized patient supplemental oxygen = # days where the 7-point ordinal scale score is equal to 4, 5, or 6.
		 Or 7-point ordinal scale score is equal to 7 if patient dies while hospitalized between Day 1-29.
		Not hospitalized patient supplemental oxygen = # days where the 7-point ordinal scale score is equal to 2 (if required to have home oxygen).

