9.4.6 Duration of hospitalization (Day 1 - Day 29; measured in days)

The total number of days with recorded use will be the sum of all reported days, regardless of whether the days occur consecutively or in disjoint intervals. Results will be summarized by descriptive statistics including medians and quartiles by treatment arm and compared between treatment groups using Wilcoxon rank sum test.

Summaries of the results of the secondary analyses are displayed in Table 11.

Table 11. Clinical study RPL554-COV-201 analysis tables - Secondary Analyses.

Table #	Table Name	Table Contents
14.2.5	Time to recovery, Day 1 - Day 29	Overall and by Treatment group
14.2.6	Proportion of patients in recovery at Day 60, ITT	Overall and by Treatment group Day 1 – Day 7 Day 1 – Day 14
14.2.7	Proportion of patients with improvement of one category using the 7-point ordinal scale from Day 1, ITT	Overall and by Treatment group Day 1 – Day 7 Day 1 – Day 14 Day 1 – Day 29
14.2.8	Proportion of patients with improvement of two categories using the 7-point ordinal scale from Day 1, ITT	Overall and by Treatment group Day 1 – Day 7 Day 1 – Day 14 Day 1 – Day 29
14.2.9	All-cause mortality, ITT	Overall and by Treatment group At Day 29 At Day 60
14.2.10	Proportion of patients alive and not in respiratory failure (invasive mechanical ventilation or extracorporeal membrane oxygenation (ECMO) at Day 29, ITT	Overall and by Treatment group Day 1 – Day 7 Day 1 – Day 14
14.2.11	Summary of the proportion of patients re- hospitalized following initiation of study medication and subsequent discharge (over 60 days), ITT	Overall and by Treatment group
14.2.12	Duration of hospitalization from Day 1 (Day 1 - Day 29; measured in days), ITT	Overall and by Treatment group
14.2.13	Change from baseline in 7-point ordinal scale at Days 7, 14 and 29, ITT	Overall and by Treatment group Baseline – Day 7 Baseline – Day 14 Baseline – Day 29
14.2.14	Total time on supplemental oxygen (Day 1 - Day 29; measured in days), ITT	Overall and by Treatment group
14.2.15	Total time of non-invasive ventilation or high flow oxygen use (post-dose Day 1 - Day 29; measured in days).	Overall and by Treatment group
14.2.16	Summary of the proportion of patients with oxygen use at Days 7, 14 and 29, ITT	Overall and by Treatment group
14.2.17	Summary of the proportion of patients with non-invasive ventilation or high flow oxygen use at Days 7, 14 and 29), ITT	Overall and by Treatment group

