Day 1 - Day 29	n		
-	Yes		
	No		

pg. 54 Confidential

⁽or discharge, whichever was first)
*7-point ordinal scale score = 1, 2, 3, 4 or 5. n = number of patients with recorded value

Table 14.2.11: Summary of Proportion of patients re-hospitalized following initiation of study medication and subsequent discharge (over 60 days), ITT

Proportion of Patients	Re-hospitalized	Enrolled (N=45)	Ensifentrine (N=30)	Placebo (N=15)
Day 1 - Day 60	ay 1 - Day 60 n			
	Yes			
	No			

n = number of patients with recorded value

Table 14.2.12: Duration of hospitalization from initiation of study medication (Day 1 - Day 29 (or discharge, whichever was first); measured in days), ITT

Days of hospitalization	Enrolled		Placebo p-value*
from Day 1	(N=45	(N=30)	(N=15)
Median (Q1 - Q3)			

^{*}Wilcoxon rank sum test

Hospitalized = # days where the 7-point ordinal scale score = 3, 4, 5 or 6.

Discharge = The patient is discharged and leaves the hospital alive.

pg. 56 Confidential

Table 14.2.13: Change from Baseline in 7-point Ordinal Scale at Days 7, 14, and 29, ITT

Change from 7-point Ordin	n Baseline in nal Scale	Enrolled (N=45)	Ensifentrine (N=30)	Placebo (N=15)
Day 7	n Mean (SD)	()	()	()
Day 14	n Mean (SD)			
Day 29	n Mean (SD)			

Computed from Day 1 scale minus Day 7, Day 14, and Day 29 scale accordingly (or discharge) (or discharge, whichever was first)

pg. 57 Confidential

Table 14.2.14: Total time on Supplemental Oxygen (Day 1 - Day 29; measured in days), ITT

Days of Suppl	emental Oxygen	Enrolled	Ensifentrine	Placebo
(Scale=4)		(N=45)	(N=30)	(N=15)
Day 1 - 29	Median (Q1 - Q3)			

Hospitalized patient: 7-point ordinal scale score = 4, 5, or 6. Or 7-point ordinal scale score is equal to 7 if patient dies while hospitalized between Day 1-29.

Not hospitalized patient supplemental oxygen = # days where the 7-point ordinal scale score is equal to 2 (if required to have home oxygen).

pg. 58 Confidential

Table 14.2.15: Total time of non-invasive ventilation or high flow oxygen use (post-dose Day 1 - Day 29 (or discharge, whichever was first); measured in days)

Days of non-invasive ventilation or High Flow Oxygen Use (Scale=5)		Enrolled (N=45)	l Ensifentrine (N=30)	Placebo (N=15)
Day 1 - 29	Median (Q1 - Q3)			

Non-invasive ventilation or high flow oxygen use = # days where the 7-point ordinal scale score is equal to 5 or 6. Or 7-point ordinal scale score is equal to 7 if patient dies while hospitalized between Day 1-29.

pg. 59 Confidential

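### Total hospital days are counted from ordinal scores that are daily only until discharge, so a readmitted patient is undercounted, although SAP 9.4.6 and 8.5 suggest that readmission days should count

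*SAP*

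**What the plan says.** **The count.** SAP 7.2, Table 5, names the endpoint as total time of hospitalization between Day 1 and Day 29 and defines it as "Hospitalized = # days where the 7-point ordinal scale score is equal to 3, 4, 5 or 6". A score of 7 also counts if the patient dies in hospital in that window.

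**The analysis text.** SAP 9.4.6 adds up all reported days "regardless of whether the days occur consecutively or in disjoint intervals" and compares the arms with a Wilcoxon rank sum test. SAP 8.5 says that a discharged patient with no further hospitalization data is taken as not readmitted.

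**The shell.** The title of example Table 14.2.12 sets the window as "Day 1 - Day 29 (or discharge, whichever was first); measured in days), ITT".

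**When scores exist.** Protocol 8.1 sets the daily record: "Starting on Day 1 to discharge, Day 29 or withdrawal of consent, site staff will record on an eCRF daily the following information". After that, the scale is scored at single contacts. For the discharge contact, Protocol 1.3 says that "contact with the patient will take place 4 to 10 days after discharge from hospital within the 29-day treatment period". Protocol 8.5 adds "Day 29 Contact: 26 to 32 days after first dose of study medication", and a further contact around Day 60.

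**What is known about readmission.** Protocol Table 15 collects on the Follow-up eCRF "Any incidence of re-admission to the hospital following a 24-hour period of discharge (date and duration) that is related to COVID-19". SAP Table 5 names the re-hospitalization question only for the separate endpoint on the proportion readmitted.

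**The concern.** The endpoint is called total time, and the analysis text provides for separate intervals, which for hospital days arise essentially from readmission. The variable that Table 5 counts is nearly blind to readmission. A programmer who follows Table 5 or the shell gives a readmitted patient roughly the length of the first stay. In a rank test, a patient with a long total stay is then placed among the short ones.

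Hospitalization is a stated secondary objective, and this endpoint gets a p-value. If one arm had earlier discharges followed by more readmissions, the recorded count would show the benefit of the first and miss most of the cost of the second. With two rules in one SAP, the choice between them could also be made after the data are seen.

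**Working it through.** The plan gives no power, effect size or readmission rate for this endpoint, so there is no figure of its own to reproduce. The check counts days under each rule, then looks at the effect on ranks and on the test.

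**1. Days that a readmission can add under Table 5.** After discharge, the only scored days that can fall within Days 1 to 29 are the discharge contact and the Day 29 contact. The maximum gain is two days, whatever the length of the second stay. The carry-forward rule for total-time endpoints in SAP 8.5 names oxygen and non-invasive ventilation, not hospital days.

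**2. One patient under each rule.** Hypothetical patient: in hospital Days 1 to 5, discharged Day 5, readmitted Days 8 to 20.
- Second stay: 20 − 8 + 1 = 13 days.
- Discharge contact window: Day 5 + 4 to Day 5 + 10, that is Days 9 to 15, wholly inside the readmission.

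| Rule | Days counted |
|---|---|
| Shell 14.2.12, stop at discharge | 5 |
| Table 5, contact not scored | 5 |
| Table 5, contact scored in the readmission | 5 + 1 = 6 |
| 9.4.6 with the Follow-up eCRF duration | 5 + 13 = 18 |

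**3. Effect on the rank.** A second hypothetical patient, in hospital Days 1 to 6 and readmitted Days 11 to 20, counts as 6 days (shell), 6 or 7 (Table 5) or 6 + 10 = 16 (total). This patient was placed among 44 simulated stays, log-normal with log SD 0.6, limited to 3 to 29 days (assumed). Protocol 4.3 cites a median stay of 10 to 13 days in survivors; 6 is added as a shorter case.

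| Assumed median stay | Mean rank of 45 at 6 days | Mean rank of 45 at 16 days |
|---|---|---|
| 6 | 20.4 | 42.5 |
| 10 | 8.1 | 34.8 |
| 13 | 4.4 | 28.1 |

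**4. How many patients.** The readmission rate r is an assumption. Expected number = 45 × r; chance of at least one = 1 − (1 − r)^45.
- r = 5%: 2.25 patients; 90%.
- r = 10%: 4.5 patients; 99%.
- r = 20%: 9 patients; over 99.9%.

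**5. Effect on the comparison.** Simulated at 30 v 15 with a two-sided 5% Wilcoxon test and 1,500 runs per row. Readmission was assumed to start 2 to 7 days after discharge and last 5 to 12 days, cut at Day 29. Index-only days stand for the shell; total days include the readmission. Each cell gives results for median stays of 6 and 10 days. Differences are active minus placebo means.

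| Readmission, active v placebo | First stays | Rejection, index only | Rejection, total | Difference, index only (days) | Difference, total (days) |
|---|---|---|---|---|---|
| 10% v 10% | equal | 4.5%, 6.1% | 4.5%, 5.7% | −0.02, −0.04 | −0.03, −0.03 |
| 20% v 5% | equal | 4.4%, 4.1% | 9.5%, 7.1% | −0.04, 0.07 | 1.18, 1.13 |
| 5% v 20% | equal | 4.9%, 4.5% | 10.3%, 7.3% | 0.02, 0.00 | −1.21, −1.07 |
| 20% v 5% | about 26% shorter on active (exp(−0.3) = 0.74) | 30.7%, 31.8% | 6.7%, 9.9% | −1.74, −2.81 | −0.51, −1.57 |

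With equal readmission and equal first stays, the rule makes no material difference. With unequal readmission it does. In the last row, the chance of a significant result is about 31% on index days and 7% to 10% on total days.

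**The case against.** The case for the plan is substantial. Table 5 is introduced with a pointer to further definitions in Section 8, and Section 8.5 presumes no readmission only when later hospitalization data are missing. That implies that available data count. Section 9.4.6 sums disjoint intervals in terms. The contradicting text is an example shell, and its discharge clause recurs in many other shells, including Day 29 status tables, so it looks like boilerplate. Readmission has its own endpoint, a descriptive summary of proportion and duration in SAP 9.4.2.1, and Table 14.2.11. The analyses are exploratory and the pilot is unpowered. The protocol's label, duration of hospitalization from Day 1, could also mean the index stay.

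Most of this stands and limits the point. A reader might infer that readmission days vanish with no means of recovery. The documents do not support that: the follow-up contacts can add a day or two, the protocol collects the date and duration of COVID-related readmissions, and 9.4.6 would admit them. A reader might also infer that the Wilcoxon result is biased as planned. That needs readmission to differ by arm, and no document suggests that it does. Nor do the last-dose days listed in shell 14.2.2 show how long patients stayed, since study medication can stop while the patient remains in hospital.

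Two things are not answered. No sentence puts the Follow-up eCRF durations into the hospital-day count, and the 8.5 rule itself refers to days recorded on available assessments, which are not daily after discharge. Separate reporting of readmission does not correct the ranks in this test.

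**Conclusion.** The point holds as an inconsistency with a numerical consequence. Total days appear intended, Table 5 names a source that cannot supply them, and the example shell excludes them. Following Table 5 or the shell, the first worked patient counts as 5 or 6 days instead of 18, and the second moves down by about 22 to 27 places of 45 (42.5 − 20.4 = 22.1; 34.8 − 8.1 = 26.7; 28.1 − 4.4 = 23.7).

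The undercount for a readmitted patient follows from the data collection schedule alone. Its effect on the treatment comparison rests on assumptions that the documents do not give: the readmission rate, its timing and length, the spread of stays and, above all, a difference between arms. The primary endpoint, recovery at Day 29, is unaffected. The SAP should be corrected because this secondary endpoint is tested and the rules give different results.

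**What to change.** - In SAP Table 5 and 9.4.6, define hospital days as days from Day 1 to the discharge date (Discharge eCRF) plus the days of each readmission, from the date and duration on the Follow-up eCRF (Protocol Table 15), all cut at Day 29.
- Keep the existing treatment of in-hospital deaths: score 7 counted, death handled as worst case. A purely date-based count would otherwise turn an early death into a short stay.
- Remove the discharge clause from the title of shell 14.2.12.
- State the limit of the data: only COVID-related readmissions after 24 hours out of hospital are captured. Other readmissions and earlier returns are not.
- If the index stay was intended instead, rename the Table 5 endpoint and delete the disjoint-interval sentence from 9.4.6.

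The choice should be recorded before database lock. The cost is SAP wording and one date-based derivation. No new data are needed for COVID-related readmissions.
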